8. ASSESSMENTS

8.1. EFFICACY ASSESSMENTS

Tumor response will be evaluated locally by the Investigator according to RECIST, v1.1 (**Section 17.6**).

All potential sites of tumor lesions will be assessed at screening, the following should be performed:

- A CT scan with IV contrast of chest, abdomen and pelvis is the preferred technique. If there is concern about radiation exposure, an MRI may be used instead of a CT.
- In subjects with a history of asymptomatic brain metastases, a brain MRI or CT scan
- If clinically indicated, a whole-body bone scan (i.e., if bone metastases are suspected or known at baseline). A whole-body bone imaging method may be used per local standard of care (e.g., Tc99m bone scan, fluorodeoxyglucose-positron emission tomography [FDG-PET], sodium fluoride-positron emission tomography [NaF PET] scan or whole-body bone MRI).

Skeletal lesions identified on a whole-body bone scan at baseline, which are not visible on the chest, abdomen, or pelvis CT (or MRI) scan should be imaged at baseline using localized CT, MRI, or X-ray.

As far as possible, the same method of assessment of each lesion should be used at screening and for all visits, for consistent comparison.

During the Main study period, all post-screening assessments should be performed every 6 weeks (± 7 days) from the first dose for the first 12 weeks of treatment; except for first tumor evaluation for which the time-window allowed is day 42 ± 7 days from first dose. Then, every 8 weeks thereafter until disease progression, subject decision, withdrawal of consent, initiation of subsequent anticancer therapy, subject is lost to follow-up, death or defined end of study as described in **Section 5.7**.

During the Study extension period, all assessments should be performed every 12 weeks (± 7 days), until disease progression, subject decision, withdrawal of consent, initiation of subsequent

anticancer therapy, subject is lost to follow-up, death or defined end of study as described in **Section 5.7**.

If a subject discontinues study treatment for reasons other than disease progression, tumor assessments must continue to be performed (as per local and central review) every 6 weeks (first 12 weeks) then every 8 weeks during the Main study period and every 12 weeks during the Study extension period (as per local review), until the start of new anti-cancer therapy, disease progression, death, lost to follow-up, subject decision or withdrawal consent.

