#### 9.1.2. Dates and period

*Date of first administration of study treatment* is derived as the first date when a non-zero dose of any study drug was administered and recorded on the eCRF.

*Date of last administration of study treatment* is defined as the last date when a non-zero dose of any study drug was administered and recorded on the eCRF. Note: if at a given analysis time point, the patient has a start date but with no end date and no EOT page is filled-in, the patient will be

considered as ongoing and the end date will be imputed to the cut-off date for the calculation of treatment duration.

*Last contact date* will be derived for patients (known to have died or not) at the analysis cut-off. Imputed date (e.g. analysis cut-off date programmatically imputed to replace the missing end date of a dose administration record) will **not** be considered for the determination of last contact date. Only dates associated with patient visits or actual examinations of the patient will be used in the derivation. If after derivation, the last contact date is posterior to the cut-off date, then the last contact date will be taken to be the cut-off date. Last contact date will only be derived using the latest complete date among the following:

- Start/end date of study medication with non-missing dose (doses of 0 are allowed);
- RECIST assessment date with evaluation marked as “done”;
- Laboratory/PK collection date with sample collection marked as “done”;
- Vital sign date with non-missing parameter value;
- Cardiac evaluation date with non-missing parameter value;
- ECG evaluation date with non-missing parameter value;
- Ophthalmologic evaluation date with non-missing parameter value;
- Physical examination date with non-missing parameter value;
- Questionnaire evaluation date with non-missing parameter value;
- Performance status date with non-missing performance status;
- Start/end date of adverse events with non-missing/non-“None” verbatim term and outcome different from “Fatal” and grade less than 5
- Start date of fatal AE (i.e. outcome “Fatal” and grade 5) when the Start date is strictly before the end date
- Start/end date of antineoplastic therapies administered after study treatment discontinuation with non-missing medication/procedure term;
- Date of contact in survival status when the patient is marked as alive;

- Treatment assigned date.

*FPFV used for analysis* will be defined as the earliest date of first study treatment administration.

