**This rule will be based on the distance between the last adequate TA date and the event date.**

Let D1 be the largest distance (relative to the last adequate TA date) that a patient can have a tumor assessment and not be classified as having missed an assessment. Let D2 be the largest distance (relative to the last adequate TA date) that a patient can have a tumor assessment and not be classified as having missed two assessments. If the distance exceeds threshold D1 or D2 then the analysis will assume one or two missing TAs, respectively.

The threshold D1 will be defined as the protocol specified interval between the TAs plus the protocol allowed window around the assessments. Similarly, the threshold D2 is defined as two

times the protocol specified interval between the TAs plus the protocol allowed window around the assessments.

As per protocol, post-screening assessments are expected to be performed every  $A=6$  weeks ( $\pm B=7$  days) from the first dose for the first 12 weeks of treatment ( $I=84$  days); except for first tumor evaluation for which the time-window allowed is day 42 +7 days from first dose, then every  $X=8$  weeks ( $\pm Y=7$  days) thereafter until disease progression, subject decision, withdrawal of consent, initiation of subsequent anticancer therapy, subject is lost to follow-up, death or defined end of study.

Therefore:

- if the last adequate tumor assessment before the event date is performed on or before study day 21 ( $=7*A/2$ ) then  $D_1=49 (=A*7+B)$  days and  $D_2=91 (=2*A*7+B)$  days;
  - This accounts for the scenario where the last adequate tumor assessment is the baseline assessment. This also allows for the rare instance where an additional assessment occurred early in the study.
- if the last adequate tumor assessment before the event date is performed between study day  $M+1$  (where  $M= I- (1.5*A)*7$ ) to study day  $N$  then  $D_1=A*7+2*B$  days and  $D_2=(A+X)*7+B+Y$  days;
  - Day  $N$  is calculated as  $N = I- (0.5*A)*7$ .
  - This accounts for the scenario where only the first scheduled assessments after the last adequate tumor assessment occur prior to month  $I$ .
- if the last adequate tumor assessment before the event date is performed between study day  $N+1$  and study day  $P$  then  $D_1=X*7+B+Y$  days and  $D_2=2*X*7+B+Y$  days;
  - Day  $P$  is calculated as  $P = I+ (0.5*X)*7$ .

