#### **14.2.4. PFS based on investigator assessment**

PFS based on local review will be calculated and summarized using the KM method. The corresponding median PFS with 95% CI, 25th and 75th percentiles (Brookmeyer and Crowley 1982, Klein and Moeschberger 1997), as well as PFS estimated probabilities at selected time points (every 2 months up to 14 months) will be provided with 95% CI (Kalbfleisch and Prentice 2002) for the FAS and ES.

Progressive disease and death from any cause will be considered as events. If death or PD is not observed, the PFS will be censored at the date of last adequate tumor assessment prior to the cutoff date or new anti-tumoral treatment intake. However, if a PFS event is observed after more than 1 missing or inadequate tumor assessment, it will be censored at the last adequate tumor assessment. If a PFS event is observed after a single missing or non-adequate tumor assessment, the actual date of event will be used.

Censoring rules to be applied to the PFS endpoint are described in detail in

Table 12. Censor status will be summarized.

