**Table 12: Censoring rules for PFS**

In the below table, “new antineoplastic therapy” refers to any additional secondary antineoplastic medication or anti-cancer surgery or radiotherapy.

	Situation	Event Date	Outcome
No baseline tumor assessments			
A1	No baseline assessment and death after the second scheduled post-baseline tumor assessment, or no death	Date of first study treatment administration	Censored
A2	No baseline assessment and death on or before the second scheduled post-baseline tumor assessment	Date of death	Event
No post-baseline tumor assessments (without new antineoplastic therapy given)			
B1	Death on or before the second scheduled post-baseline tumor assessment	Date of death	Event
B2	Death after the second scheduled post-baseline tumor assessment or no death	Date of first study treatment administration	Censored
With baseline and post-baseline tumor assessments (without new antineoplastic therapy given prior progression or death without progression observed)			
C1	Progression with zero or one missed/inadequate tumor assessment prior to progression	Date of progression	Event
C2	Death but no progression, with zero or one missed/inadequate tumor assessment prior to death	Date of death	Event
D1	Progression but two or more consecutively missed/inadequate tumor assessments prior to progression	Date of last adequate tumor assessment*	Censored
D2	Death without progression, but two or more consecutively missed/inadequate tumor assessments prior to death	Date of last adequate tumor assessment*	Censored
E	No progression, no death	Date of last adequate tumor assessment*	Censored
F	Treatment discontinuation due to ‘Disease progression’ without documented progression, i.e. clinical progression based on investigator claim	N/A (not considered as an event, patient without documented PD should be followed for progression after discontinuation of treatment)	Information ignored
Initiation of new antineoplastic therapy given prior progression or death without progression observed			
G	New antineoplastic therapy started before progression or death	Date of last adequate tumor assessment prior to initiation of new antineoplastic therapy*	Censored
H	No post-baseline tumor assessment and new antineoplastic therapy started prior to a death	Date of first study treatment administration	Censored

\* tumor assessment with non-missing and non-unknown overall lesion response, as defined in section 9.3.

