**Table 17: Censoring rules for TST**

In the below table, “subsequent antineoplastic therapy” refers to any additional secondary antineoplastic medication or anti-cancer surgery or radiotherapy.

	Situation	Event Date	Outcome
A	Initiation of subsequent antineoplastic therapy	Start date of subsequent antineoplastic therapy	Event
B	Death at any time after the first study treatment administration	Date of death	Event
C	Patient alive without starting a subsequent antineoplastic therapy	Date of last contact	Censored

PFS after next line of treatment (PFS2) will be defined as the time from the first study treatment administration to the earlier of death at any time after the first study treatment administration or progression after the start of subsequent anticancer therapy.

PFS2 will be described using survival curves according to the Kaplan Meier method and reporting estimated median (in months) with 95% CI, 25th and 75th percentiles and KM estimated probabilities with corresponding 95% CIs at several time points (every 2 months up to 14 months).

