**Table 18: Censoring rules for PFS2**

In the below table, “subsequent antineoplastic therapy” refers to any additional secondary antineoplastic medication or anti-cancer surgery or radiotherapy.

	Situation	Event Date	Outcome
A	Progression after start of subsequent antineoplastic therapy	Date of progression	Event
B1	Death at any time after the first study treatment administration and before the start of any subsequent antineoplastic therapy, after zero or one missed/inadequate tumor assessment while on the Study	Date of death	Event
B2	Death at any time after the first study treatment administration and before the start of any subsequent antineoplastic therapy, after 2 or more missed/inadequate tumor assessments while on the Study	Date of last contact	Censored
B3	Death after the start of any subsequent antineoplastic therapy	Date of death	Event
C	Patient alive and without progression on their subsequent antineoplastic therapy	Date of last contact	Censored

	Situation	Event Date	Outcome
D	Patient alive, without starting a subsequent antineoplastic therapy	Date of last contact	Censored

Procedures related to COVID-19 pandemic (e.g. quarantine, patient isolation, testing, etc) will be listed on an individual basis, with reported term, MedDRA Preferred Term (PT) and Lowest Level Term (LLT), and dates, day relative to first study treatment administration and status with respect to the study treatment period. Procedures related to COVID-19 are reported in the eCRF with a prefix “COVID19” and will be coded using appropriate MedDRA codes. Prefix will not be displayed in the listing.

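### Table 18 row B2 censors recorded deaths that the PFS2 definition counts as events, although missed on-study scans cannot hide a PFS2 event

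*SAP*

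**What the plan says.** The text of SAP 15.11 measures PFS2 from first dose to "the earlier of death at any time after the first study treatment administration or progression after the start of subsequent anticancer therapy". It gives no exception for missed scans.

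Table 18 then splits deaths before subsequent therapy into two rows. Row B1 makes the death an event if it came "after zero or one missed/inadequate tumor assessment while on the Study". Row B2 covers the same death "before the start of any subsequent antineoplastic therapy, after 2 or more missed/inadequate tumor assessments while on the Study" and censors it at last contact. Row B3 counts every death after subsequent therapy has started, whatever scans were missed.

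SAP 9.1.2 says that the last contact date "will be derived for patients (known to have died or not) at the analysis cut-off". It is built mainly from visits, examinations and contacts while the subject was alive.

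For PFS, the missed-scan exception is written into the text of SAP 14.2.4: "if a PFS event is observed after more than 1 missing or inadequate tumor assessment, it will be censored" at the last adequate scan. Table 12 row D2 repeats it: "Death without progression, but two or more consecutively missed/inadequate tumor assessments prior to death". A sensitivity analysis without the exception is planned for PFS (Table 13). None is stated for PFS2.

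**The concern.** The definition and the table give different outcomes for the same subject, and the reason for the PFS exception does not transfer to PFS2. A subject in row B2 leaves the risk set at or just before a death that the sponsor has on record. That is informative censoring, and it tends to push the PFS2 curve up.

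It also makes the endpoints inconsistent with one another. The same death is an event for OS, and for time to subsequent therapy (Table 17 row B), but is censored for PFS2. In a subject with no subsequent therapy, PFS2 time and OS time are the same quantity. Censoring only the former can let the estimated PFS2 curve rise above the OS curve, which the definitions do not allow.

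**Working it through.** **1. Can a missed scan hide a PFS2 event in these subjects?**

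| | PFS (14.2.4, Table 12) | PFS2 (15.11, Table 18) |
|---|---|---|
| Progression before subsequent therapy | Event | Not an event |
| Progression after subsequent therapy starts | Not counted: follow-up censored when new therapy starts | Event (row A) |
| Death before subsequent therapy | Event, unless two or more scans missed | Event by definition; censored by row B2 |
| What a run of missed scans can hide | An earlier event | Nothing that counts |

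Row B2 is restricted to subjects who died before any subsequent therapy. For them death is the only possible PFS2 event.

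**2. How are missed scans counted?** Table 18 does not say. The only counting rule in the SAP (9.3) is "based on the distance between the last adequate TA date and the event date". Two scans count as missed when that distance exceeds 91, 112 or 126 days, for a last adequate scan on study days 1–21, 22–63, or 64 and later (Table 8). Under Protocol 8.1 scans run "every 8 weeks thereafter until disease progression, subject decision, withdrawal of consent, initiation of subsequent anticancer therapy", loss to follow-up, death or end of study. If the distance rule is applied to row B2, a subject who progresses on study, receives nothing further and dies more than 126 days after that scan is treated as having missed two scans, although none was due.

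**3. Size, simple bound.** The SAP gives no PFS2 figure to reproduce and no rate of row B2 deaths, so every input from here on is an assumption. If PFS2 is exponential and a share f of events is recoded as censored, the estimated hazard falls by the factor 1 − f and the median rises by 1/(1 − f). With n = 90 and complete follow-up:

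- 2 deaths: 1/(1 − 2/90) = 1.023
- 5 deaths: 1/(1 − 5/90) = 1.059
- 9 deaths: 1/(1 − 9/90) = 1.111

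**4. Size, simulated Kaplan-Meier medians.** Assumptions: 90 subjects, exponential PFS2, row B2 deaths drawn from events later than day 126, last contact 0 to 3 months before death, 4,000 trials per setting. The 12 to 25 months follows from even entry between Nov 2018 and Dec 2019 and a cut-off of 27 Dec 2020.

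| Deaths recoded | Complete follow-up, true medians 9, 12, 15 months | Follow-up 12–25 months, true medians 9, 12 months |
|---|---|---|
| 0 | 1.000 | 1.000 |
| 2 | 1.021–1.027 | 1.033–1.045 |
| 5 | 1.051–1.067 | 1.080–1.115 |
| 9 | 1.095–1.119 | 1.146–1.222 |

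Entries are mean ratios of the median with row B2 applied to the median without it. With only 2 deaths recoded, the median does not move at all in 36–48% of trials (complete follow-up) or 13–27% (12–25 months).

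A separate simulation took follow-up of 12 to 24 months and recoded a share of the events after month 3 to censoring half a month before death. With a true median of 12 months, the typical estimate is 11.7 months at 0%, 12.4 at 5%, 12.9 at 10%, 13.5 at 15% and 14.3 at 20%. The 12-month probability rises from 0.50 to 0.55 over the same range.

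**5. Size under the distance reading.** 126 days is 126/30.4375 = 4.14 months. If the median time from the progression scan to death without further therapy is s months, the chance of dying more than 126 days after that scan is 2^(−4.14/s): 0.238, 0.384 and 0.488 for s = 2, 3 and 4. If 10% to 30% of 90 subjects progress and get no further therapy, the expected number runs from 9 × 0.238 = 2.1 to 27 × 0.488 = 13.2. Simulated with 12 to 25 months of follow-up (3,000 trials; median 6 months to progression; in treated subjects a 1-month gap, then a median of 4 months to the PFS2 event), 1.5 to 7.6 such deaths are observed on average and the median ratio is 1.019 to 1.082.

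**The case against.** A censoring table that refines a short definition is normal in this SAP: the endpoint definitions of PFS and DOR in 6.3.2 also omit the missed-scan exception, which 14.2 and its tables add. That explains how row B2 may have arisen, but 15.11 has no linking text and the rationale still does not carry over.

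A long gap might also conceal unrecorded subsequent therapy and progression, since both are known only from follow-up contacts. This is fair as far as it goes. However, row B3 and Table 17 take no such precaution, and row B2 by its own terms concerns deaths before any such therapy.

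Row B2 lacks the word requiring the missed scans to be consecutive, so read literally it is wider than Table 12 row D2. Little rests on this. The SAP's PFS text omits the word too, and under the distance rule the missed scans are consecutive by construction.

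The distance reading is also open to dispute. A scan that was not due is arguably not missed, and 9.3 describes a schedule that ends at progression. It shows an ambiguity in Table 18 and is not needed for the main point.

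Finally, the sizes are hypothetical. Nothing in the documents suggests as many as nine such deaths, and zero is possible. All of that stands, and it limits the importance of the point, not its correctness.

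**Conclusion.** Row B2 is wrong as written. It contradicts the definition in the same section, and the censoring is informative for no gain, because no PFS2 event can be hidden in these subjects. The direction is upward. The size depends on how many such deaths occur: none gives no effect, and 2 to 9 of 90 give roughly 2–12% on the median with complete follow-up or 3–22% with 12 to 25 months, under exponential PFS2 and the other assumptions stated. The distance reading would add subjects who missed no scheduled scan, with a rise of about 2–8%.

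The consequence is small. PFS2 is a descriptive summary in 15.11, is not among the endpoints listed in the protocol or in SAP 6.3, and is exploratory under SAP 8. The cORR test, its type I error and the sample size are untouched. Confidence is high in the contradiction and the rationale, and much lower in any particular size.

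**What to change.** In Table 18, make row B2 an event at the date of death. Rows B1 and B2 then merge into one row covering any death before subsequent therapy, which matches 15.11 and removes the need to count missed scans for PFS2. Writing the exception into 15.11 would also make text and table agree, but would keep the bias. If the sponsor wants the current rule, it can be kept as a labelled sensitivity analysis.

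The cost is one table row, minor reprogramming and possibly a slightly shorter reported median. The SAP is already at version 5, and its Appendix 5 puts all listed analyses except PK and resource use into the Stage 2 output. If PFS2 results have already been seen, the change should be labelled post hoc.

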## 16. QUALITY OF LIFE ANALYSIS

Quality of Life will be evaluated through the EORTC QLQ-C30, EQ-5D-5L QoL and PGIC questionnaires on the FAS.

The number of patients completing the questionnaires and the number of missing or incomplete assessments will be summarized for each time window. Compliance for each questionnaire is described in

Table 19.

**Table 19: Patient Reported Outcomes Compliance**

Questionnaire	Status		
	Missing	Incomplete assessment	Complete assessment
EORTC QLQ-C30	0 question answered	1 to 29 questions answered	30 questions answered
EQ-5D-5L	0 question answered	1 to 5 questions answered	6 questions answered
PGIC	0 question answered	NA	1 question answered

## 16.1. EORTC QLQ-C30 SCORING

Following the European Organisation for Research and Treatment of Cancer (EORTC) recommendations , fifteen scores will be derived from the initial 30 questions of the QLQ-C30 questionnaire:

a global health-related quality of life scale,

five functional scales: physical, role, cognitive, emotional, social,

nine symptom scales: nausea and vomiting, pain, fatigue, dyspnoea, insomnia, appetite loss, constipation, diarrhoea, financial difficulties.

They will be the health-related quality of life parameters of the analysis on QLQ-C30 questionnaire.

Of note, a higher value in functional scales (resp. Global Health Status) will reflect a better level of function (resp. quality of life), but for “symptoms” scales a higher value will reveal a deterioration of the condition.

Each scale in the EORTC QLQ-C30 questionnaire will be scored (0 to 100) according to the EORTC recommendations in the EORTC QLQ-C30 Scoring Manual. The scoring method is summarized below. In this summary  $Q_i$  refers to the  $i^{\text{th}}$  question on the EORTC QLQ-C30, and score value correspondence is ["1" = "Not at All", "2" = "A Little", "3" = "Quite a Bit", "4" = "Very Much"] for Q1 to Q28.

